3.1 Eligibility Criteria

3.1.1 Lower risk MDS patients (IPSS-R score ≤ 3.5 at diagnosis) who have progressed or are refractory to/intolerant of prior therapy and meet one of the following categories:

- RBC transfusion dependent according to IWG criteria must either be unresponsive to prior ESA therapy or have an EPO level > 500
- Prior HMA therapy
- Patients with the following cytopenias who otherwise are felt to require treatment per the treating physician:
 - Platelets $< 50k/uL$
 - ANC < 500 cells/uL
- Patients with MDS with isolated del(5q) (“5q- syndrome”) must have progressed on or not tolerated lenalidomide
- Patients who are not felt to be candidates for or lack other standard treatment options. Patients with prior luspatercept exposure are eligible.
- Patients with dysplastic type CMML (WBC $< 13,000$ cells/uL) meeting the above criteria are eligible; responses will be assessed using MDS criteria

3.1.2 Age ≥ 18 years. Because no dosing or adverse event data are currently available on the use of MGB453 in participants < 18 years of age, children are excluded from this study, but will be eligible for future pediatric trials.

3.1.3 ECOG performance status ≤ 2 (see Appendix A).

3.1.4 Participants must have adequate organ and marrow function as defined below within 21 days of treatment:

- Total bilirubin ≤ 2 mg/dL (unless due to Gilbert’s in which case it must be < 3 mg/dL)
- AST(SGOT)/ALT(SGPT) $\leq 3 \times$ institutional ULN
- Creatinine clearance ≥ 30 mL/min/1.73 m² (by MDRD calculation)

3.1.5 Human immunodeficiency virus (HIV)-infected participants on effective anti-retroviral therapy with undetectable viral load over the prior 6 months are eligible for this trial.

3.1.6 Participants with known history or current symptoms of cardiac disease, or history of treatment with cardiotoxic agents, should have a clinical risk assessment of cardiac function using the New York Heart Association Functional Classification. To be eligible

for this trial, participants should be class 2B or better.

3.1.7 Ability to understand and the willingness to sign a written informed consent document.

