
a: Albumin, alkaline phosphatase, total bilirubin, direct bilirubin, bicarbonate or CO₂, BUN, calcium, chloride, creatinine, glucose, LDH, phosphorus, potassium, magnesium, total protein, SGOT [AST], SGPT [ALT], sodium, uric acid, amylase, lipase.
 
b: Serum pregnancy test (women of childbearing potential, WOCP). At screening, a serum pregnancy test (serum β-HCG) must be performed within 3 days before the first dose for WOCP. During the study, a urine / serum pregnancy test should be done at Day 1 of each cycle for WOCP (except Cycle 1 if a pregnancy test had been performed within 72 hours of the first dose) and at EOT visit. A pregnancy test (serum or urine) should be performed every month during the safety follow-up period for WOCP (until day 150). If the patient is not coming to the clinic during the safety follow-up, it can be performed at home or at a local doctor's office, and the results will be communicated to the site staff.
 
c: Bone marrow biopsy and aspirate should be performed at baseline, cycle 3 day 1 ±3 days, and then within 7 days of cycle 5 day 1, at end of treatment, and as clinically indicated. Standard institutional testing including cytogenetics and molecular testing is recommended.
 
d: Off-treatment evaluation. The in-person visit has a window of ±3 days; additional safety follow-up is required through day 150. Note: for IND/IDE trials, follow up visits or other contact are required in order to identify SAEs during the 30 days following the end of study treatment. After end of treatment visit, patients should be followed per section 5.7 for survival and progression.
 
e: Bone marrow assessment for cycle 7 and cycle 11 may be done up to 7 days prior to the start of the treatment cycle. If a patient has a bone marrow assessment within 1 cycle of the planned assessment (e.g. cycle 6 or cycle 10) this may be used for the study assessment. A bone marrow for research samples will be performed on cycle 1 day 3 (window day 3-6).
 
f: Bone marrow samples for correlative studies will be collected at baseline, at cycle 3 day 1, and EOT for both NGS testing and for cytof analysis.
 
g: Blood pressure, heart rate, and temperature will be performed at screening and then as clinically indicated. . Bone marrow biopsy on cycle 5 day 1 will only require Cytof samples to be obtained.
 
h: On C1D1, total bilirubin, direct bilirubin, creatinine, SGOT [AST], SGPT [ALT], and INR should continue to meet inclusion criteria. Baseline values will be those assessed on C1D1
 
i: Follow up to evaluate for progression and survival may be ±7 days from those noted (day 30, 150, 250, and 1 year). Safety evaluations must be through 150 days after the last dose of MBG453. The safety follow up can be done by telephone call or visit. The information collected is kept as source documentation. All SAEs reported during this time period must be reported as described in Section 7.3. Documentation of attempts to contact the subject should be recorded in the source documentation.
 
j: TSH, free T3, and free T4 should be obtained during screening. TSH should be monitored regularly (at selected visits) during treatment and as clinically indicated. If TSH is abnormal, then test free-T3 and free-T4.
 
k: Rapid Heme Panel for NGS should be collected as part of standard of care with bone marrow biopsies at screening, C3D1 (+/-3 days), and EOT/progression. In the event of a dry tap, peripheral blood may be substituted.
											

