11.1. Antitumor Effect – MDS

Complete remission (CR): patients must have a bone marrow with ≤ 5% myeloblasts and with normal maturation of all cell lines. Persistent dysplasia may be noted. Blood counts over a duration of at least 4 weeks should show a hemoglobin ≥ 11 g/dL, platelets ≥ 100,000/uL, and absolute neutrophil count ≥ 1000/uL, without circulating blasts in the peripheral blood.

Partial remission (PR): over a duration of at least 4 weeks, all CR criteria (if abnormal prior to treatment) except:

1. Bone marrow blasts have decreased $\geq 50\%$ over pre-treatment levels but are still $> 5\%$, if elevated at baseline
2. Cellularity and morphology are not considered relevant

Marrow Complete Remission (mCR): over a duration of at least 4 weeks, bone marrow showing $\leq 5\%$ myeloblasts and with a decreased of $\geq 50\%$ over pre-treatment levels. If the peripheral blood counts show evidence of hematologic improvement responses, these will be noted in addition to the marrow CR.

Complete Remission with Partial Hematologic Recovery: $< 5\%$ blasts in the bone marrow and partial recovery of peripheral blood counts (platelets $> 50 \times 10^9/L$ and ANC $> 0.5 \times 10^9/L$).

Stable disease (SD): failure to achieve at least PR, but without evidence of progression for > 8 weeks.

Hematologic Responses According to the 2006 Hematologic Response Criteria:

Hematologic Improvement: HI is assessed in addition to CR/PR/mCR/SD.

1. Erythroid response: pretreatment level < 11 g/dL, showing a hemoglobin increase by ≥ 1.5 g/dL over at least 8 weeks
2. Platelet response: pretreatment level $< 100,000/uL$; showing:
 - a. Absolute increase $\geq 30,000$ if baseline $> 20,000$
 - b. Absolute increase $> 20,000$ and by at least 100% increase if baseline $< 20,000$
3. Neutrophil response: pretreatment level $< 1000/uL$, showing an absolute increase $> 500/uL$ and at least a 100% increase

Transfusion Independence: pretreatment requirement of at least 4U RBC within an 8 week period for a Hgb < 9 g/dL, no transfusions needed over an 8 week period

Hematologic Responses According to Proposed 2018 Hematologic Response Criteria:

We will also collect responses according to the proposed 2018 criteria. Patients will be categorized at baseline based on transfusion needs in the prior 16 weeks into three groups:

1. Non-transfusion Dependent (NTD): 0-2 RBCs in 16 weeks

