2. Low Transfusion Burden (LTB): 3-7 RBCs in at least 2 transfusion episodes, maximum of 3 in a given 8 week period
3. High Transfusion Burden (HTB): ≥ 8 RBCs in 16 weeks, ≥ 4 in 8 weeks

IWG 2018 hematologic responses will include:

1. Erythroid Response: pretreatment Hgb level < 10 d/dL
 - a. NTD: At least 2 consecutive Hgb measurements ≥ 1.5 g/dL for a period of minimum 8 weeks in an observation period of 16 to 24 weeks compared with the lowest mean of 2 Hgb measurements (apart from any transfusion) within 16 weeks before treatment onset

- b. LTB: HI-E in LTB patients corresponds to transfusion independence, defined by the absence of any transfusions for at least 8 weeks in an observation period of 16-24 weeks, compared with 16 weeks prior to treatment
- c. HTB:
 - i. Major response: Major HI-E response in HTB patients corresponds to transfusion independence, defined by the absence of any transfusions over a period of minimum 8 weeks in an observation period of 16-24 weeks compared with 16 weeks prior to treatment
 - ii. Minor response: Minor HI-E response in HTB patients is defined as a reduction by at least 50% of RBCs over 16 weeks
2. Platelet response: pretreatment level < 100,000/uL; showing:
 - a. Absolute increase \geq 30,000 if baseline > 20,000
 - b. Absolute increase > 20,000 and by at least 100% increase if baseline < 20,000Increments of platelets will be reported for patients with pretreatment platelets >100k
3. Neutrophil response: pretreatment level < 1000/uL, showing an absolute increase > 500/uL and at least a 100% increase. Increments of neutrophils will be reported for patients with a pretreatment ANC > 1000.

Overall Response Rate

The overall response rate (ORR) will be defined as CR + PR + CRh + HI + TI. It will be reported using both the 2006 and 2018 criteria above but the primary endpoint will be based on the 2006 criteria.

Patients not meeting one of the above criteria are considered to have a failed response (see “Failure,” below).

The following response measures may be assessed in addition to/subsequent to the above.

Cytogenetic response:

1. Complete response is the disappearance of the chromosomal abnormality without the appearance of new ones
2. Partial response is at least 50% reduction of the chromosomal abnormality

Progression of disease:

1. For patients with <5% blasts: \geq 50% increase in blasts to > 5% blasts
2. 5-10% blasts: \geq 50% increase in blasts to > 10% blasts

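### The 2006 erythroid response that feeds the primary ORR has no transfusion-free condition, so a patient still receiving RBC transfusions could be scored as a responder

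*Combined protocol and SAP*

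**What the plan says.** Section 11.1 sets the components: "The overall response rate (ORR) will be defined as CR + PR + CRh + HI + TI". ORR is reported under both criteria sets, but "the primary endpoint will be based on the 2006 criteria". Section 13.1 refers to 11.1 for the components and takes the best response in the first 6 months. Section 13.5 only points back to 13.1.

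Within the 2006 list, the erythroid part of HI reads "Erythroid response: pretreatment level < 11 g/dL, showing a hemoglobin increase by ≥ 1.5 g/dL over at least 8 weeks". The separate transfusion-independence (TI) route reads "Transfusion Independence: pretreatment requirement of at least 4U RBC within an 8 week period for a Hgb < 9 g/dL, no transfusions needed over" an 8-week period.

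The 2018 list in the same section treats transfusion differently. For non-transfusion-dependent (NTD) patients the hemoglobin rise is "compared with the lowest mean of 2 Hgb measurements (apart from any transfusion) within 16 weeks before treatment onset". For low-burden (LTB) patients response is transfusion independence, "defined by the absence of any transfusions for at least 8 weeks in an observation period of 16-24 weeks", and the major response in high-burden (HTB) patients is defined in the same way.

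On the population, section 3.1.1 admits transfused patients: "RBC transfusion dependent according to IWG criteria must either be unresponsive to prior ESA therapy or have an EPO level > 500". Section 5.5 restricts growth factors in order to protect the hematologic endpoint but does not restrict transfusion, and section 7.3.5 treats transfusion as routine care of the disease. The section 10 calendar collects the previous 16 weeks of transfusions and those given on study.

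**The concern.** RBC transfusion raises the quantity that the erythroid rule measures, and it is background care for part of this population. The rule that decides the primary endpoint names only a starting level, a rise and a duration. It does not say that the rise must occur without transfusion, that hemoglobins drawn soon after a transfusion are set aside, or that the pretreatment value must be unaffected by transfusion. It is also not confined to untransfused patients: TI is an additional route to response and does not replace the hemoglobin rule for those who need blood.

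The trial is single-arm, with a fixed cut of 6 responders in 22. A response produced by transfusion would be read as drug activity, and no control arm would show the same effect.

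**Working it through.** **1. The rules side by side (section 11.1).**

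| Rule | Used for primary ORR | Transfusion-free response window | Baseline apart from transfusion |
|---|---|---|---|
| 2006 erythroid | yes | no | no |
| 2006 TI | yes | yes, 8 weeks | not applicable (unit count) |
| 2018 NTD | no | not stated | yes |
| 2018 LTB, HTB major | no | yes, at least 8 weeks | not applicable (transfusion history) |

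The only hemoglobin-rise rule in the primary endpoint has neither safeguard.

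**2. Can the printed rule be met under transfusion?** Take a hypothetical patient with a pre-transfusion hemoglobin of 7.5 g/dL who is transfused so that visit values lie at 9.0 to 9.5 g/dL for 8 weeks. The rise is 9.0 − 7.5 = 1.5 g/dL at the lowest, so the line is satisfied. The rule fixes neither the number nor the timing of measurements. The calendar schedules blood counts weekly in cycles 1–2, on days 1 and 15 in cycles 3–4, and on day 1 only from cycle 5.

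**3. Who has no TI route?** TI entry needs at least 4 units in 8 weeks for a hemoglobin below 9 g/dL. Patients on 1–3 units per 8 weeks do not meet it, so for an erythroid response they depend on the hemoglobin rule alone. If their baseline was raised by a recent transfusion, they could become transfusion-free without showing a 1.5 g/dL rise and be missed.

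**4. The plan's own operating characteristics.** Inputs from section 13.1: stop if there is at most 1 response in 10; otherwise enrol 12 more and reject at 6 or more in 22; null rate 0.15, alternative 0.35.

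P(declare active) = Σ over x = 2…10 of Bin(x; 10, p) × P(Bin(12, p) ≥ 6 − x)

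At p = 0.15 the terms are:

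- x = 2: 0.2759 × 0.0922 = 0.0254
- x = 3: 0.1298 × 0.2642 = 0.0343
- x = 4: 0.0401 × 0.5565 = 0.0223
- x = 5: 0.0085 × 0.8578 = 0.0073
- x ≥ 6: 0.0014

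The sum is 0.0907. At p = 0.35 the result is 0.804. Both agree with the stated 0.09 and 0.80.

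**5. Sensitivity to misclassification.** Assume that a share m of true non-responders is credited because of transfusion. The apparent rate is then 0.15 + 0.85m, and the expected number of credited patients in 22 is 22 × 0.85 × m. The documents give no value for m.

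| m (assumed) | Apparent rate | Expected credited patients in 22 | P(pass stage 1) | P(declare active) |
|---|---|---|---|---|
| 0 | 0.150 | 0 | 0.456 | 0.091 |
| 2% | 0.167 | 0.4 | 0.517 | 0.135 |
| 5% | 0.1925 | 0.9 | 0.601 | 0.218 |
| 10% | 0.235 | 1.9 | 0.720 | 0.387 |

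These shares apply to all non-responders. Patients may also enter on platelets or neutrophils and need not be transfused. If half of the non-responders were transfused (assumption), m = 5% would mean 10% of the transfused ones.

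**The case against.** Five points weigh on the other side.

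- **The cited source.** The opening of section 11 bases assessment on the published 2006 IWG criteria, with named modifications, so the printed line may be shorthand. That source cannot be checked here. But 11.1 writes out its own rule, and a reader applying it finds no transfusion condition. If one is meant to carry over, 11.1 should say so.
- **Transfusion dependence counts as loss of HI.** Section 11.1 lists it under progression or relapse from HI, which shows that the protocol regards the two as incompatible. It does not bar the initial scoring, and a best response within 6 months would stand.
- **A stable pattern would not produce a rise.** A patient on an unchanged transfusion schedule, sampled at similar times, would not be expected to show a sustained 1.5 g/dL increase. This stands: the hypothetical case needs a low pre-transfusion baseline set against supported on-study values. It limits the likely frequency but does not close the gap.
- **Discrepancies would be visible.** ORR is also reported under the 2018 criteria and transfusions are recorded. That helps interpretation, but the go/no-go count still rests on the 2006 list.
- **Errors run both ways.** The sensitivity table models upward error only.

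Three stronger readings are tempting, and the documents do not support them. A reader might infer that footnote h of the calendar ("Baseline values will be those assessed on C1D1") fixes the baseline hemoglobin at a single C1D1 value; the footnote concerns bilirubin, creatinine, transaminases and INR and does not name hemoglobin. A reader might infer that the 2018 list also protects on-study hemoglobins; the NTD text protects only the baseline. And a reader might infer that true responders are lost generally; those who meet TI entry and then need no transfusion for 8 weeks still count through TI.

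**Conclusion.** The gap is real and lies in the operative text of the primary endpoint. As printed, the 2006 erythroid line could credit a patient who is still being transfused, and nothing elsewhere in the documents prevents it. Upward bias in ORR is possible, not demonstrated, and its frequency cannot be derived from the documents.

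The design leaves little room for such error. About one credited patient in 22 (m = 5%) would take the false-positive probability from 0.091 to 0.218, and about two (m = 10%) to 0.387; at m = 2% it would be 0.135. These figures rest on assumed values of m, a true rate of 0.15 and no offsetting missed responders. The opposite error is confined to patients below TI entry whose baseline was raised by transfusion. The stated type I error and power are correct for the rule as designed and are not in dispute. The wording should be changed before responses are scored.

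**What to change.** In section 11.1, amend the 2006 erythroid line so that:

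1. the rise of at least 1.5 g/dL is scored only if no RBC transfusion was given during the 8-week response window, for all patients;
2. the pretreatment hemoglobin is taken from values not influenced by transfusion, using an exclusion interval after transfusion that is fixed in advance;
3. patients who meet TI entry can still qualify through TI.

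The first condition must apply to everyone. Sending only TI-entry patients to the TI rule would leave those on 1–3 units per 8 weeks on an unprotected hemoglobin rule.

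This is a scoring change only and does not affect when patients are transfused. It needs new wording in 11.1 and a link from the response derivation to the transfusion record that the calendar already provides. Sample size, visits, decision boundaries and stated error rates stay as they are. The cost is that a few patients will lack an evaluable hemoglobin, and the reported ORR may be slightly lower.

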Given the evidence of blood count responses in patients with advanced myeloid disease, and the favorable toxicity profile of MBG453 monotherapy, there is rationale to study MBG453 monotherapy for the treatment of lower-risk MDS. For those patients who are RBC transfusion dependent, they must have progressed after ESA therapy or be unlikely to respond to ESA therapy,

characterized by an EPO level >500, who are not felt to be candidates for or lack other treatment options. In addition, given early activity, there is particular interest in neutrophil and platelet responses to MBG453. These remain significant complications of MDS, with infectious and bleeding events identified as common causes of death from MDS. Therefore, patients with lower-risk MDS characterized by other cytopenias are also eligible if they require therapy, have cytopenias that can be assessed for IWG response, and are not eligible for or have progressed on other standard therapy.

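### Platelet response in section 11.1: for baselines below 20,000 the 100% condition can never operate, which points to a drafting slip, and a baseline of exactly 20,000 has no rule

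*Combined protocol and SAP*

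**What the plan says.** Section 11.1 applies to patients with pretreatment platelets below 100,000/uL and gives two branches. Branch (a) is "Absolute increase $\geq 30,000$ if baseline $> 20,000". Branch (b) is "Absolute increase $> 20,000$ and by at least 100% increase if baseline $< 20,000". The 2006 and 2018 lists print the same two branches.

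The rule feeds the primary endpoint. "The overall response rate (ORR) will be defined as CR + PR + CRh + HI + TI", and although the rate is reported under both sets, "the primary endpoint will be based on the 2006 criteria". Hematologic improvement (HI) includes the platelet response.

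Patients with very low platelets can enter: section 3.1 lists "Platelets $< 50k/uL" among its categories. Section 2.3 adds that "there is particular interest in neutrophil and platelet responses to MBG453".

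Section 13.1 sets the decision rule: stop with 1 or fewer responses in 10 patients, and reject a null rate of 0.15 with 6 or more in 22. The stated type I error is 0.09, and the stated power is 0.80 at a true rate of 0.35.

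**The concern.** Two conditions joined by *and* should each be able to exclude someone. In branch (b) the phrase "and by at least 100% increase if baseline" excludes nobody, because the absolute-rise condition already implies it. That suggests the first condition is not worded as intended.

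The obvious candidate is that 20,000 is a level to be exceeded, starting from below it, with the 100% condition as an additional requirement. Under that reading both conditions do some work and the bar is lower for the most thrombocytopenic patients.

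Separately, (a) needs a baseline above 20,000 and (b) a baseline below it, so the value 20,000 is unassigned.

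The choice of reading decides whether some patients with very low platelets count as responders in a trial whose boundaries turn on single patients. If it is left open until responses are counted, it will be made with outcomes known.

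**Working it through.** **1. The plan's own figures.** Inputs from section 13.1: n1 = 10, continue with 2 or more responses, n = 22, reject with 6 or more. P(reject | p) = sum over x = 2 to 10 of Bin(x; 10, p) × P(Bin(12, p) ≥ 6 − x). At p = 0.15 this is 0.0907, and at p = 0.35 it is 0.8040. The stated 0.09 and 0.80 reproduce.

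**2. The 100% condition cannot bind.** Let b be the baseline and d the rise. If b < 20,000 and d > 20,000, then d/b > 20,000/20,000 = 1, which is more than 100%. As a check, baselines of 1,000 to 19,000 in steps of 1,000 were crossed with on-treatment counts of 0 to 100,000 in steps of 500. Removing the 100% condition changed 0 classifications. The smallest relative rise among responders was 20,500/19,000 = 107.9%.

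**3. Comparison with other rules in section 11.1.**
- The neutrophil rule applies below 1,000/uL and has the same two-part form: "showing an absolute increase > 500/uL and at least a 100% increase. Increments of neutrophils". There the relative condition does bind: 800 to 1,400 is +600 but 600/800 = 75%, so it fails.
- The blast-progression rules use a relative rise to a level, and in the lowest band the baseline cut-off and the level are the same number (5%). Branch (b) also uses one number twice, which fits that pattern if 20,000 is a level.

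**4. What the printed rule does below 20,000.**
- Doubling: d = b < 20,000, so it never qualifies.
- Tripling: d = 2b, which exceeds 20,000 only if b > 10,000. So 8,000 to 24,000 fails, and 12,000 to 36,000 (+24,000) passes.
- 10,000 to 28,000 is +18,000 (+180%) and fails. 6,000 to 25,000 is +19,000 (+317%) and fails.

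**5. Printed rule against the level reading.** The printed rule needs a count above b + 20,000. The level reading, an assumption here, needs a count above 20,000 and at least 2b.

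| Baseline | Printed: count | Level reading: count | Difference |
|---|---|---|---|
| 5,000 | > 25,000 | > 20,000 | 5,000 |
| 8,000 | > 28,000 | > 20,000 | 8,000 |
| 10,000 | > 30,000 | > 20,000 | 10,000 |
| 12,000 | > 32,000 | ≥ 24,000 | 8,000 |
| 15,000 | > 35,000 | ≥ 30,000 | 5,000 |
| 19,000 | > 39,000 | ≥ 38,000 | 1,000 |

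The gap is widest at 10,000, where the required rise halves from > 20,000 to > 10,000. No responder under the printed rule is lost under the level reading.

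**6. Baseline of exactly 20,000.** Neither branch applies. Even 20,000 to 90,000 is not a platelet response as written.

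**7. Sensitivity of the decision to one patient, at a true rate of 0.35.**
- P(exactly 1 of 10) = 10 × 0.35 × 0.65^9 = 0.072.
- P(pass stage 1 and end at exactly 5 of 22) = sum over x = 2 to 5 of Bin(x; 10, 0.35) × Bin(5 − x; 12, 0.35) = 0.071.
- Together, about 14% of such trials end one response short of a boundary.

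**8. Illustration only.** The share of patients affected is not in the documents. If the printed rule lowered a true rate of 0.35 by 0, 1, 2, 3 or 5 percentage points, power would be 0.804, 0.778, 0.749, 0.718 or 0.650.

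**The case against.** A redundant condition does no harm. Apart from the value 20,000, the printed rule classifies every baseline without ambiguity, so it can be applied as it stands. The cited criteria are not among the documents, so nothing here shows which wording is right. This stands. The internal evidence supports a query and a conditional rewording, but not a statement that patients are being misclassified.

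A reader might infer that any tripling from a low baseline is missed. That is not so: tripling from above 10,000 passes.

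A reader might also infer that these patients are denied the primary response. The response rate is a composite, and only the platelet HI route is closed. Erythroid HI, neutrophil HI and transfusion independence stay open to patients with those cytopenias, and CR, PR and CRh are judged on their own thresholds. The remaining worry is narrower. A patient whose only evaluable cytopenia is platelets, and whose count stays in the disputed range (below 40,000), has none of the first three routes and is below the platelet thresholds for CR and CRh.

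A third tempting inference is that the observed rate is biased low against the 0.15 null. The plan does not give the platelet definitions used in the studies behind that null, so the comparison cannot be made.

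Finally, if the printed bar is too strict, the error runs toward missing activity, whereas loosening it makes responses easier in a single-arm trial. The printed platelet rule states no minimum duration, unlike the erythroid rule, so under the level reading a single count moving from 10,000 to 20,001 would qualify. This is a real cost of the rewording.

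**Conclusion.** The point holds as a definitional defect in a component of the primary endpoint. Two parts are certain from the text: the 100% condition in branch (b) never operates, and a baseline of exactly 20,000 has no rule. That 20,000 was meant as a level is a well-supported inference, not an established fact.

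For baselines below 20,000 the two readings differ by up to 10,000 in the count required. The effect on the response rate, type I error or power cannot be quantified, because the documents do not give the share of patients with such baselines or their expected changes. The power range above rests on assumed losses. The stated design figures are correct for the response probabilities they assume, and nothing here disturbs them.

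The point should be settled because one patient can move the result across either boundary and the correction is small.

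**What to change.** Before the stage 1 count, and in both the 2006 and 2018 lists of section 11.1:

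1. Assign a baseline of exactly 20,000 to a branch, for example by making branch (a) apply at 20,000 or more. A patient starting at 20,000 would then need a count of at least 50,000.
2. Check branch (b) against the cited 2006 and 2018 criteria, and state whether 20,000 is the size of the rise or a level to exceed.
3. If it is a level, reword (b) as an increase from below 20,000 to above 20,000 and by at least 100%. If it is a rise, delete the 100% condition, since it has no effect.

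This costs two lines in each list and needs no new data. The downside of the level wording is that the required rise falls by up to half (at a baseline of 10,000, from > 20,000 to > 10,000), so more patients with a baseline below 20,000 would count as responders.

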
11. MEASUREMENT OF EFFECT

Response to therapy will be assessed based on the proposal for the modification of the International Working Group (IWG) response criteria in myelodysplasia (Cheson et al., 2006), but modified to include complete remission with partial hematologic improvement CRh (Bloomfield et al., 2018), and the 2018 proposed update for hematologic responses and transfusion independence (TI) (Platzbecker et al., 2019). Patients with dysplastic-type CMML will use MDS risk-stratification and response assessment criteria.

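### Section 11.1 gives platelet and neutrophil HI, and CRh, no duration and no rule for transfused or growth-factor-supported counts, yet each alone makes a primary-endpoint responder

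*Combined protocol and SAP*

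**What the plan says.** Section 11.1 writes out its own 2006 response list.

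- **With a duration.** For CR: "Blood counts over a duration of at least 4 weeks should show a hemoglobin". PR and marrow CR also carry 4 weeks. Erythroid improvement must hold "g/dL over at least 8 weeks", and transfusion independence means "no transfusions needed over an 8 week period".
- **Without a duration.** The platelet item reads "Platelet response: pretreatment level $< 100,000/uL$; showing" and then gives increments only. The neutrophil item asks for a patient "showing an absolute increase $> 500/uL$ and at least a 100% increase". CRh asks for marrow blasts below 5%, platelets above 50 × 10⁹/L and ANC above 0.5 × 10⁹/L, with no period and no stated change from baseline.

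The components combine as follows: "The overall response rate (ORR) will be defined as CR + PR + CRh + HI + TI", and "the primary endpoint will be based on the 2006 criteria". Section 13.1 scores the best response in the first 6 months.

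Section 11 opens with a general reference: "Response to therapy will be assessed based on the proposal for the modification of the International Working Group (IWG) response criteria in myelodysplasia". Section 5.5 bars growth factors but permits short use in acute illness. Section 7.3.5 treats platelet transfusion as routine care in this disease. The study calendar records transfusions. None of these places, nor sections 13.5 and 13.7, says how a count taken under such support is scored.

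**The concern.** The two lineages without a duration are the ones in which section 2.3 declares particular interest. Because the endpoint is a best response, a single high count scores and a later fall does not undo it. The count could be a fluctuation, follow a platelet transfusion or occur during growth factor. The erythroid item also does not exclude hemoglobin supported by transfusion.

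The rule reaches beyond patients entered for low platelets or neutrophils. Section 3.1.1 sets those entry limits at 50k and 500, whereas 11.1 opens platelet improvement below 100k and neutrophil improvement below 1000. A patient entered for anemia with platelets of 80k would score on one count of 110k. If that patient has ANC above 500 and marrow blasts below 5%, the written CRh limits are already met before treatment.

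With 22 patients and success at 6 responses, two assessors who read 11.1 differently could reach opposite conclusions about the trial.

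**Working it through.** **1. Durations side by side (2006 list, section 11.1)**

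| Component | In ORR | Stated duration |
|---|---|---|
| CR, PR | yes | at least 4 weeks |
| Marrow CR | no | at least 4 weeks |
| CRh | yes | none |
| Erythroid HI | yes | at least 8 weeks |
| Transfusion independence | yes | 8 weeks |
| Platelet HI | yes | none |
| Neutrophil HI | yes | none |

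The calendar schedules 13 post-baseline blood counts through cycle 6 day 1, or 14 with cycle 7 day 1. Read literally, any one could qualify.

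**2. Reproducing the design.** Inputs from section 13.1: stop if 1 or fewer of 10 respond; otherwise add 12; declare activity at 6 or more of 22. With X ~ Bin(10, p) and Y ~ Bin(12, p):

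R(p) = Σ(x = 2 to 10) P(X = x) · P(Y ≥ 6 − x)

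At p = 0.15:
- x = 2: 0.2759 × 0.0922 = 0.0254
- x = 3: 0.1298 × 0.2642 = 0.0343
- x = 4: 0.0401 × 0.5565 = 0.0223
- x = 5: 0.0085 × 0.8578 = 0.0073
- x ≥ 6: 0.0014

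The sum is 0.0907, against the stated 0.09. At p = 0.35 the same formula gives 0.804, against the stated 0.80. The plan's figures are correct.

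**3. Sensitivity to the no-effect rate under the definition actually scored**

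| No-effect rate | Chance of declaring activity |
|---|---|
| 0.13 | 0.051 |
| 0.14 | 0.069 |
| 0.15 | 0.091 |
| 0.16 | 0.116 |
| 0.17 | 0.144 |
| 0.20 | 0.246 |

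**4. Nearness to the cut-off.** At 0.15, the chance of continuing and finishing on exactly 5 responses is Σ(x = 2 to 5) P(X = x) · P(Y = 5 − x) = 0.099.

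**5. One certain false responder, the other 21 at 0.15**
- In stage 1: Σ(y = 1 to 9) P(Bin(9) = y) · P(Bin(12) ≥ 5 − y) = 0.192
- In stage 2: Σ(x = 2 to 10) P(X = x) · P(Bin(11) ≥ 5 − x) = 0.170
- Position equally likely among the 22: (10 × 0.1919 + 12 × 0.1702) / 22 = 0.180

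With the other 21 at 0.13, the weighted figure is 0.116, against 0.051 without the false responder.

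**6. What 0.15 refers to.** Section 13 bases 0.15 on five trials. By title, two are in thrombocytopenia, one is in anemia with thrombocytopenia and none is in neutropenia. The only rate shown is 13% in section 2.1, and no response definitions are given. Whether 0.15 already includes single-count responders cannot be seen.

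**The case against.** The strongest reply is that section 11 ties scoring to the cited 2006 criteria. If that source states a duration, 11.1 is an incomplete summary and assessors already have the rule. This stands in part: it rules out calling single-count scoring the established rule. It does not settle the matter, because 11.1 sets its own thresholds and writes durations for the neighbouring items, so silence can fairly be read as no duration.

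Other safeguards exist. Growth factor is limited to urgent, short use and relayed to the overall principal investigator. Transfusions are recorded. Loss of improvement is defined in 11.1 and duration of response is reported, so brief responses would be visible. These lower the frequency or expose the problem afterwards, but they set no scoring rule and do not reverse a best response.

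For CRh, the word recovery in its name suggests a change from baseline. No change is specified.

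A reader might infer that the true type I error is above 0.09, or is 0.180. The documents do not support that. The 0.180 is conditional on one certain false responder, and 0.15 may already allow for such patients; it also exceeds the 13% shown. Nor do the documents establish 8 weeks as the only possible duration, since the same list uses 4 weeks elsewhere.

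**Conclusion.** The gap in the written endpoint is real and should be fixed. Platelet HI, neutrophil HI and CRh lack a duration, CRh lacks a baseline condition, and supported counts have no scoring rule. Mending HI alone would leave the literal reading open through CRh.

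The design calculation itself is sound. The 0.09 holds only if the no-effect rate under the definition applied is 0.15. One false responder is enough to move the chance of declaring activity from 0.091 to 0.180, assuming that responder is certain, equally likely to be any of the 22, and the rest respond independently at 0.15. How many to expect depends on count variability, transfusion and growth factor use, none of which the documents quantify. The inflation may be nil, small or material. That uncertainty, and the possibility that the cited criteria supply a duration, keep this below a must-fix.

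**What to change.** In section 11.1:
- Give platelet and neutrophil HI a minimum sustained duration, reconciled with the cited 2006 criteria. Eight weeks would match the protocol's own erythroid and transfusion-independence items.
- Give CRh a duration, and require that the patient did not already meet it at baseline.
- State that platelet counts shortly after platelet transfusion, ANC during or shortly after growth factor, and transfusion-supported hemoglobin do not count toward response, and give the windows.
- State whether the duration must end by month 6 or only begin by then.

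In section 13, confirm that 0.15 and 0.35 refer to this definition.

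The planned blood counts, transfusion records and medication records suffice for the HI duration and the support rules. Sample size, cut-offs and visits do not change. The cost is that brief or late responses no longer count. With an 8-week rule ending by day 168, a rise first seen at day 140 cannot qualify (140 + 56 = 196). If the true ORR under the stricter definition were 0.33, 0.32 or 0.30 instead of 0.35, power would be 0.75, 0.72 or 0.65 instead of 0.80. Letting the 8 weeks end after month 6 loses fewer late responses but could delay the primary report by up to 8 weeks.
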